involvement than women in the controlled ovarian stimulation group ( $p = 0.02$ ). After a mean follow-up of approximately 5 years, the study confirmed the absence of survival difference between the two groups, with an HR for recurrence after controlled ovarian stimulation of 0.77 (95% CI, 0.28-2.13;  $p = 0.61$ ). Although the numbers were limited, the authors performed several subgroup analyses showing that, apparently, neither *BRC A* mutation status ( $p = 0.57$ ), nor hormone-receptor status ( $p = 0.75$ ) nor undergoing controlled ovarian stimulation before or after breast surgery ( $p = 0.44$ ) seemed to affect survival in the controlled ovarian stimulation group [25]. Taking into account these results, all major international guidelines consider this strategy as standard in breast cancer patients [2,13–15]. However, during oncofertility counseling, it should be made clear that limited data are available to strongly support the safety of this procedure in breast cancer patients.

Of note, the first studies investigating the use of letrozole for assisted reproductive technology (ART) showed a potential increased risk of congenital cardiac and musculoskeletal anomalies in the newborns [26]; hence, its manufacturer issued a warning to physicians to stop using letrozole for this purpose in pre-menopausal women. However, subsequent studies did not confirm these findings [27–29]. Recently, a large Japanese study including 3,136 natural cycles and 792 letrozole-induced cycles investigated the risk of major congenital anomalies, pregnancy and neonatal outcomes with the use of letrozole in patients undergoing ART [30]. The study showed that the risk of miscarriage was significantly lower in women treated with letrozole (adjusted odds ratio [OR], 0.37; 95% CI, 0.30-0.47;  $p < 0.001$ ). Furthermore, the overall risk of major congenital anomalies was similar between the two groups (natural cycle 1.5% vs. letrozole 1.9%; adjusted OR, 1.24; 95% CI, 0.64-2.40;  $p = 0.52$ ), as well as the risk for any specific organ system malformation. Finally, no difference in all the other pregnancy and neonatal outcomes was observed between the two groups [30]. Hence, although these results support the safety of letrozole for assisted reproductive technology (ART), in some countries like France this compound cannot be used as part of controlled ovarian stimulation.

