### 3.2. Data collection

For all consecutive eligible patients included in the study, anonymized data will be entered into ad hoc electronic Case Report Forms (eCRF). The following information will be collected:

1) Baseline characteristics (at study inclusion): BMI; smoking habit; age at menarche; use of birth control pills; prior children before breast cancer diagnosis; history of spontaneous or induced abortion; prior treatment for infertility; prior gynecological surgery and/or medical history with possible impact on fertility; baseline AMH value.

- 2) Breast cancer history: date of diagnosis; age at diagnosis; disease stage; type of breast and axillary surgery; histology; tumor size and nodal status (for patients who underwent primary systemic therapy, both clinical tumor size and nodal status before treatment initiation and pathological tumor size and nodal status at the time of surgery will be collected); grade; hormone receptor status (estrogen and progesterone receptors); HER2 status.
- 3) Treatment of the primary tumor: timing of systemic therapy administration (adjuvant or neoadjuvant); use of chemotherapy (type and number of cycles); use of endocrine therapy (type and duration); use of anti-HER2 targeted therapy (type and duration); use of radiotherapy; use of breast reconstruction surgery.
- 4) Survival status: any recurrence of invasive breast cancer including date of the event; type of recurrence of invasive breast cancer (locoregional or distant event); any second primary contralateral breast cancer including date of the event; any second primary malignancy including date of the event; date of last follow-up and/or death.
- 5) Controlled ovarian stimulation protocol: type of stimulation (follicular or random); total FSH dose; number of stimulation days; number of days with antagonist; estradiol and progesterone levels at triggering and during luteal phase (L3-L8); number of oocyte/embryo collected; number of mature oocytes collected; maturation rate; number of oocyte/embryo cryopreserved; number of patients with poor response; number of patients with stimulation failure.
- 6) Ovarian function before and after chemotherapy: treatment-induced amenorrhea; age at menopause; AMH values.
- 7) Pregnancy after breast cancer: any pregnancy including date of the event; pregnancy outcome; gestational age at delivery; pregnancy/fetal/obstetrical outcomes; breastfeeding and its duration; use and type of assisted reproductive technology.

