8) Presence of germline *BRCA* mutation or other type of germline mutations (if available): date of genetic testing; type of mutation; use and date of breast prophylactic surgery; use and date of gynecological prophylactic surgery.

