#### **4.4. Laboratory procedures for circulating tumor DNA**

Three blood samples of 10 ml should be collected in EDTA tubes; two samples will be centrifuged within 1 hour from collection, to separate plasma from peripheral blood cells, at 820g for 10 minutes at  $4^{\circ}\text{C}$ . Recover and transfer plasma (the top yellowish layer of the tube content) into new micro tubes, compatible with high-speed centrifuge. Centrifuge the plasma at maximum speed (if available 20000g is recommended) for 10 minutes at  $4^{\circ}\text{C}$ . Transfer all plasma into cryovials and stored at  $-80^{\circ}$ . The 3rd sample of whole blood will be stored directly at  $-80^{\circ}\text{C}$ . Blood and plasma samples will be shipped on dry ice to the central laboratory (Erasmus hospital) at fixed time points for evaluation.

Plasma samples will be collected at enrollment (i.e. at the time of oncofertility counseling/breast cancer diagnosis) before starting chemotherapy (and before starting controlled ovarian stimulation in patients who access oocyte/embryo cryopreservation), Then, this analysis will be repeated at the end of controlled ovarian stimulation, and at relapse or end of follow-up.

In this study, evaluation of the circulating tumor DNA (ctDNA) in the plasma will be performed. The aim is to 1) evaluate the effect of controlled ovarian stimulation on the levels of ctDNA and correlate

with risk of recurrence and 2) to evaluate the pattern of somatic mutations in young breast cancer patients.

Before performing the evaluation of ctDNA, primary tumor analysis is required. Hence, 15 representative slides (10µm) must be collected instead. Samples will be shipped to the central laboratory (Erasmus hospital) at fixed time points for evaluation.

The aim is to elucidate the biology of breast cancer in young women. Techniques will comprise but not restricted to immunohistochemistry, in situ hybridization, expression profiling and sequencing. Extraction of nucleic acids (DNA and RNA) may be required to perform these analyses.

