To evaluate the safety of performing a controlled ovarian stimulation with or without letrozole in young women with newly diagnosed breast cancer who are candidates to receive (neo)adjuvant chemotherapy, the following endpoints will be assessed:

- Invasive disease-free survival (iDFS) defined as the time from study inclusion to the first appearance of the following invasive events: local recurrence, distant metastases, contralateral or ipsilateral breast tumor, second primary malignancy, or death from any cause;
- Breast cancer-free interval (BCFI) defined as the time from study inclusion to the first appearance of the following invasive events: local recurrence, distant metastases, contralateral or ipsilateral breast tumor;
- Overall survival (OS) defined as the time from study inclusion to death from any cause;
- Kinetic of circulating tumor DNA (ctDNA) assessed before, after stimulation and during study follow-up (if disease relapse).
- Complications associated with any of the procedure used for oocyte/embryo cryopreservation.

The safety of performing controlled ovarian stimulation with or without letrozole will be evaluated in various subgroups of young women with newly diagnosed breast cancer who are candidates to receive (neo)adjuvant chemotherapy according to the following characteristics:

- Stage at diagnosis: I vs. II vs. III;
- Hormone receptor status: positive vs. negative;
- HER2 status: positive vs. negative;
- Type of exposure to chemotherapy: prior to surgery (neoadjuvant) vs. post surgery (adjuvant);
- Exposure to endocrine therapy: exposure vs. no exposure;
- Presence of *BRCA* mutation: *BRCA*-mutated vs. *BRCA*-not mutated;
- Baseline ctDNA level: present vs. absent.

The following baseline characteristics of young women with newly diagnosed breast cancer who undergo controlled ovarian stimulation with or without letrozole will be assessed:

- Body-Mass Index (BMI) and body surface;
- Smoking history;
- Age at menarche;
- Prior pregnancies (completed, induced or spontaneous abortion);
- Prior treatment for infertility;
- Prior use of birth control pills;
- Prior gynecological diseases with potential impact on reproductive potential;
- Baseline ovarian reserve and function analysis.

Furthermore, the following characteristics of protocols with or without letrozole used for controlled ovarian stimulation in young women with newly diagnosed breast cancer who are candidates to receive (neo)adjuvant chemotherapy will be evaluated:

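### In adjuvant patients, breast surgery may fall between the two ctDNA samples, and the operation date needed to separate those cases is not among the listed data

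*Combined protocol and SAP*

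**What the plan says.** Section 4.4 states the aim in causal terms: to "evaluate the effect of controlled ovarian stimulation on the levels of ctDNA" and to relate this to recurrence risk. On timing it says "Plasma samples will be collected at enrollment (i.e. at the time of oncofertility counseling/breast cancer diagnosis) before starting chemotherapy", and also before stimulation in women who have it. Then "this analysis will be repeated at the end of controlled ovarian stimulation, and at relapse or end of follow-up".

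Table 1 requires plasma at inclusion, at the end of stimulation (month 0-1) and at relapse. It requires none at the start of stimulation, so the inclusion sample is the only 'before' sample.

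Section 5 lists ctDNA kinetics as one of five safety endpoints and says that all safety analyses compare each stimulated cohort separately with the non-stimulated cohort. It plans safety subgroups by neoadjuvant versus adjuvant chemotherapy. It gives no model for ctDNA and no rule for surgery.

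Section 3.2 collects "disease stage; type of breast and axillary surgery; histology; tumor size and nodal status", and whether systemic therapy was adjuvant or neoadjuvant. The only breast operation with a listed date is in the germline-mutation item: "use and date of breast prophylactic surgery".

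**The concern.** A before/after change measures the effect of stimulation only if nothing else that moves ctDNA happens between the samples. Removing the tumour is the obvious candidate. Both draws are anchored to enrollment, stimulation and chemotherapy, and the eligibility criteria do not fix where surgery falls relative to any of these.

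If surgery lowers ctDNA, the error runs towards reassurance. A surgical fall in some women would offset a stimulation-related rise, and the pooled change would look flat or favourable. That is the wrong direction for a safety endpoint.

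The planned comparator does not evidently help. The second draw is defined by the end of stimulation, a visit that non-stimulated women do not have. Their only later plasma is at relapse or the end of follow-up.

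**Working it through.** **Any figure in the plan.** None is stated for ctDNA. The only powered figure is for mature oocytes: a difference of 1.5, SD 4.0, two-sided alpha 0.05 and power 0.80. The exact t-test gives 112.6, so 113 per cohort, with power 0.801 at 113. The figure reproduces. It is used below only as a number of pairs.

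**Which women are affected.**

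| Group | Position of surgery | Samples | Identifiable from the listed data? |
|---|---|---|---|
| Neoadjuvant | after chemotherapy | tumour in place at both | yes |
| Adjuvant, operated before enrollment | before both draws | tumour removed at both | no |
| Adjuvant, operated between draws | inside the interval | in place, then removed | no |
| Adjuvant, operated after stimulation | after both draws | tumour in place at both | no |

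The first row follows because Section 1 requires cryopreservation to be finished before gonadotoxic treatment starts, and neoadjuvant chemotherapy precedes surgery. The other three rows share one category, adjuvant, and only the operation date tells them apart.

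**Is the missing date just shorthand?** Section 3.2 asks explicitly for dates of diagnosis, recurrence, second cancers, pregnancy, genetic testing and prophylactic surgery. For the primary operation it gives only "type of breast and axillary surgery". It lists no plasma draw dates.

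**Size on the detectable share.** All inputs are assumptions, treated as independent:
- p = detectable at diagnosis, 20-50%
- f = share of women with surgery between draws, 0-60%
- c = cleared by surgery among those detectable, 50-80%

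Spurious fall = p × f × c, with no stimulation effect.

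- f = 0: 0 points
- f = 10%: 0.20 × 0.10 × 0.50 = 1 point, to 0.50 × 0.10 × 0.80 = 4 points
- f = 60%: 0.20 × 0.60 × 0.50 = 6 points, to 0.50 × 0.60 × 0.80 = 24 points

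The full range is 0 to 24 points.

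**Size on a paired test.** Assume 113 pairs, no stimulation effect, and surgery shifting the ctDNA change by d within-group SDs in a share f. Then the mean change is f × d, its SD is √(1 + f(1−f)d²), and the non-centrality is √113 × mean/SD. For f = 25% and d = 1: 0.25/√1.1875 = 0.229; × 10.63 = 2.44; chance of p < 0.05 = 68%.

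| f | d = 0.5 | d = 1 |
|---|---|---|
| 0 | 5% | 5% |
| 10% | 8% | 17% |
| 25% | 25% | 68% |
| 50% | 72% | 99.7% |

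The documents give neither f nor d. The table shows only how quickly the error grows with f.

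**The case against.** The strongest reply is that the problem may be small.

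- **The window is short.** The second draw is at month 0-1, and a Table 1 footnote provides for stimulation starting within 5 days of inclusion. An operation must fall inside that window to cause bias, and nothing in the documents says this is common. This stands, and it is why the range starts at zero. The same footnote also implies that longer gaps occur.
- **Enrollment may follow surgery.** The first draw is tied to fertility counseling as well as to diagnosis, so some adjuvant women will have both samples after the operation. This stands too, but the listed data cannot show which women they are.
- **A planned subgroup already helps.** A reader might infer that nobody can be classified. That goes too far, because neoadjuvant women are identifiable and clean.
- **The date may exist anyway.** A reader might infer that it is certainly not captured. The documents show only that Section 3.2 does not list it. The eCRF itself is not shown, and hospital records are named as source documents in Section 8.1.
- **The background is not evidence about this study.** Section 1 mentions "undergoing controlled ovarian stimulation before or after breast surgery", but for a cited single-center cohort. It shows that either order occurs in practice. It does not show that surgery falls between two blood draws here.

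A reader might also start f at 40% and infer a fall of at least 4 points (0.20 × 0.40 × 0.50). No passage supports such a floor.

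**Conclusion.** The point holds for adjuvant women. Followed as written, the plan can mix a surgical change in ctDNA into the change it would read as an effect of stimulation, and the listed variables cannot separate the two. The size is unknown: 0 to 24 percentage points on the detectable share, under assumed and independent inputs and the assumption that surgery lowers ctDNA.

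A reader might go on to infer that stimulation would be declared safe on this basis. The documents do not support that: ctDNA is one secondary, unpowered safety endpoint, and invasive disease-free survival, breast cancer-free interval and overall survival are assessed separately. The change is worth making because it is cheap and protects the reading of this endpoint.

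**What to change.** 1. Add the date of primary breast surgery and the date of each plasma draw to the Section 3.2 list and confirm both are in the eCRF.
2. In Section 5, classify each plasma sample as before or after surgery. Base the main before/after ctDNA analysis on women with no surgery between samples, stratified by tumour in place or removed, and report women with interval surgery separately.
3. Describe the result as an uncontrolled before/after change. Removing interval surgery does not supply the missing second sample in the non-stimulated cohort, so attribution to stimulation remains limited.

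Cost: two kinds of date field, a short addition to Section 5, and a smaller main ctDNA set. Adjusting for surgical status in all women would keep the numbers but rests on a modelled surgical effect, so it fits better as a supporting analysis. No treatment, visit or sample-size change is needed.

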## 5. STATISTICS

Three cohorts of patients will be prospectively included in the study (Figure 1 in the Appendix):

**1) Letrozole-stimulated cohort:** this includes all newly diagnosed breast cancer who are candidates to receive (neo)adjuvant chemotherapy and undergo oocyte/embryo cryopreservation at the Belgian participating centres.

**2) Standard-stimulated cohort:** this includes all newly diagnosed breast cancer who are candidates to receive (neo)adjuvant chemotherapy and undergo oocyte/embryo cryopreservation at the French participating centres.

**3) Non-stimulated cohort:** this includes all newly diagnosed breast cancer who are candidates to receive (neo)adjuvant chemotherapy who have access to the Fertility Clinics in all the participating centres but are not willing to undergo oocyte/embryo cryopreservation. Patient who underwent another fertility preservation procedure (ovarian tissue cryopreservation, GnRH analogues,...) are eligible in this cohort.

All the efficacy analyses will be performed to compare the letrozole-stimulated cohort and the standard-stimulated cohort. All the safety analyses will be conducted to compare separately the letrozole-stimulated cohort with the non-stimulated cohort and the standard-stimulated cohort with the non-stimulated cohort.

To evaluate the efficacy of performing a controlled ovarian stimulation with or without letrozole in young women with newly diagnosed breast cancer who are candidates to receive (neo)adjuvant chemotherapy, the following endpoints will be assessed:

- Number of mature oocytes collected (primary endpoint).
- Number of oocytes collected;
- Maturation rate: defined as ratio between the number of mature oocyte collected and total number of oocyte collected;
- Number of oocyte/embryo cryopreserved;
- Number of patients with poor response: defined as retrieval of  $\leq 4$  oocytes;
- Number of patients with stimulation failure: defined as no follicular growth after 1 week of adequate controlled ovarian stimulation administration.

The efficacy of performing controlled ovarian stimulation with or without letrozole will be evaluated also in various subgroups of young women with newly diagnosed breast cancer who are candidates to receive (neo)adjuvant chemotherapy according to the following characteristics:

- Type of stimulation: follicular vs. random;
- Hormone receptor status: positive vs. negative;
- Presence of *BRCA* mutation: *BRCA*-mutated vs. *BRCA*-not mutated.

To evaluate the safety of performing a controlled ovarian stimulation with or without letrozole in young women with newly diagnosed breast cancer who are candidates to receive (neo)adjuvant chemotherapy, the following endpoints will be assessed:

- Invasive disease-free survival (iDFS) defined as the time from study inclusion to the first appearance of the following invasive events: local recurrence, distant metastases, contralateral or ipsilateral breast tumor, second primary malignancy, or death from any cause;
- Breast cancer-free interval (BCFI) defined as the time from study inclusion to the first appearance of the following invasive events: local recurrence, distant metastases, contralateral or ipsilateral breast tumor;
- Overall survival (OS) defined as the time from study inclusion to death from any cause;
- Kinetic of circulating tumor DNA (ctDNA) assessed before, after stimulation and during study follow-up (if disease relapse).
- Complications associated with any of the procedure used for oocyte/embryo cryopreservation.

The safety of performing controlled ovarian stimulation with or without letrozole will be evaluated in various subgroups of young women with newly diagnosed breast cancer who are candidates to receive (neo)adjuvant chemotherapy according to the following characteristics:

- Stage at diagnosis: I vs. II vs. III;
- Hormone receptor status: positive vs. negative;
- HER2 status: positive vs. negative;
- Type of exposure to chemotherapy: prior to surgery (neoadjuvant) vs. post surgery (adjuvant);
- Exposure to endocrine therapy: exposure vs. no exposure;
- Presence of *BRCA* mutation: *BRCA*-mutated vs. *BRCA*-not mutated;
- Baseline ctDNA level: present vs. absent.

The following baseline characteristics of young women with newly diagnosed breast cancer who undergo controlled ovarian stimulation with or without letrozole will be assessed:

- Body-Mass Index (BMI) and body surface;
- Smoking history;
- Age at menarche;
- Prior pregnancies (completed, induced or spontaneous abortion);
- Prior treatment for infertility;
- Prior use of birth control pills;
- Prior gynecological diseases with potential impact on reproductive potential;
- Baseline ovarian reserve and function analysis.

Furthermore, the following characteristics of protocols with or without letrozole used for controlled ovarian stimulation in young women with newly diagnosed breast cancer who are candidates to receive (neo)adjuvant chemotherapy will be evaluated:

- Type of stimulation: follicular or random;
- Total follicle-stimulating hormone (FSH) dose;
- Number of stimulation days;
- Number of days with antagonist;
- Progesterone and Estradiol levels at trigger;
- Progesterone level at triggering and during luteal phase (if available).

In patients who return to the fertility clinic after the end of treatment, to evaluate the type and outcomes of assisted reproductive technology procedures used, the following endpoints will be evaluated:

- Number of patients who returned to fertility clinic;
- Type of assisted reproductive technology procedures used;
- Number of embryos transferred;
- Pregnancy rate: defined by  $\beta$ -hCG determination 14 days after embryo transfer;
- Clinical pregnancy rate: defined as the presence of at least one gestational sac at the time of the first ultrasound examination by the eight week of gestation;
- Implantation rate per embryo transfer: defined as the ratio between the number of visible sacs 4 weeks after embryo transfer and the number of embryos transferred.

In patients with a clinically confirmed pregnancy obtained with assisted reproductive technology procedures after the end of treatment, pregnancy, fetal and obstetrical outcomes of the pregnancies will be evaluated. The following endpoints will be evaluated:

- Miscarriage rate;
- Live birth rate per embryo transfer: defined as the number of births of live infants beyond viability (> 24 weeks);
- Twinning rate;
- Premature delivery: <37 weeks of gestation;
- Malformation rate with number and types of malformations;
- Obstetrical complication rate with number and types of complications.

Finally, to evaluate the impact of anticancer therapies (chemotherapy with or without endocrine therapy with or without anti-HER2 agents) on patients' ovarian function, the following endpoints will be evaluated:

- Incidence of treatment-induced amenorrhea one year after the end of chemotherapy;
- Incidence of treatment-induced amenorrhea two years after the end of chemotherapy;

- Incidence of treatment-induced amenorrhea five years after the end of chemotherapy;
- Age at menopause defined as no menstrual period for more than 12 months irrespectively of menstrual resumption after chemotherapy;
- AMH values one year after the end of chemotherapy;
- AMH values two years after the end of chemotherapy;
- AMH values five years after the end of chemotherapy.

The impact of anticancer therapies on patients' ovarian function will be evaluated in various subgroups of young breast cancer patients according to:

- Age: <30 vs. 30-35 vs. > 35;
- Type of chemotherapy received: anthracycline- and taxane-based vs. taxane-based vs. others;
- Number of months of chemotherapy received: <4 months vs. > 4 months;
- Exposure to platinum agents: use vs. no use.
- Exposure to endocrine therapy: use vs. no use.
- Exposure to anti-HER2 therapy: use vs. no use.
- Presence of *BRCA* mutation: *BRCA*-mutated vs. *BRCA*-not mutated.

The sample size has been estimated based on the study primary endpoint (i.e. number of mature oocytes collected). With 113 patients in the standard-stimulated cohort and 113 in the letrozole-stimulated cohort, assuming a mean number of mature oocytes collected of 6.1 in the standard-stimulated cohort, the study will have a power of 0.80 to reject the null hypothesis of equal means when the population mean difference is 1.5 mature oocytes collected (estimating a mean number of mature oocytes collected of 7.6 in the letrozole-stimulated cohort) with a standard deviation for both groups of 4.0 and with a significance level (alpha) of 0.05 using a two-sided two-sample equal-variance t-test. Considering that approximately one out of three (1:3) eligible patients counseled to

undergo controlled ovarian stimulation for oocyte cryopreservation before starting anticancer treatments will accept the procedure, it is estimated to enroll 339 patients in the non-stimulated cohort.

Patients demographic, clinical and pathologic baseline characteristics will be compared in the three cohorts using chi-square test or Fisher Exact test for categorical variables and Wilcoxon rank-sum test or t-test for continuous variables, as appropriate.

Dicothomous outcomes will be compared using univariate and multivariate logistic regression models. Time-to-event outcomes will be estimated and plotted using Kaplan-Meier methods. Survival rates will be compared using log-rank test and Cox proportional hazards models for univariate and multivariate analysis, respectively.

All tests will be two-sided and p-values of  $< 0.05$  will be considered statistically significant.

